#### 8.9 \* PROCEDURES / METHODS: (REQUIRED)

Describe the research methods and study activities taking place at each site (e.g. what will participants be asked to do and what will members of the study team do?). If there will be multiple participant groups or study sites, explain what will happen with each group or study sites. If some of the activities would occur even if the person were not in the study, as in the case of treatment or tests performed for diagnostic purposes, clearly differentiate between those activities that will be done solely for research purposes and those that are happening as part of routine care. Please call our office at [contact] and ask to speak to someone on the Expedited Review team if you need help differentiating between what parts are research and what parts aren't.

##### **Aim 1. To examine the relationship that emotional reactivity has with mental health symptoms in older adults**

##### **Methods**

###### ***Laboratory Assessment of Emotion***

**Tasks.** We will use a laboratory-based approach to measure emotional reactivity (i.e., ANS reactivity, facial expression, and subjective experience) in response to film clips. After sitting quietly through a 60-second pre-film resting baseline period, participants will watch a 90-second film clip that elicits either a negative or positive emotion. For example, the film clips will depict a doctor cleaning earwax from a girl's ear (disgust), babies playing (love), sweeping views of broad landscapes (awe), and a woman reading a sad letter from an admirer (sadness). After film viewing, participants will be asked questions about their subjective experience.

**ANS Physiology.** We will obtain continuous recordings of the following ANS measures: (1) skin conductance level, (2) pre-ejection period, (3) respiratory sinus arrhythmia, (4) heart rate, (5) finger pulse amplitude, (6) finger pulse transmission time, (7) respiration period, (8) respiration depth, and (9) finger temperature. The participant will sit in a chair while the study staff first cleans the area where the EKG sensors will be placed with rubbing alcohol and light exfoliating gel. This is done to remove dead skin cells from the area that the sensors will be placed. Then electrode gel will be placed on the back of the sensors, and the sensors will be placed on the participant. For measures of breathing, a breathing belt will be placed around the participant's midsection, ensuring it is not too tight for the participant. For sensors placed on the hand, electrodes and electrode gel will be placed on the fingers. Mean baseline levels will be used to investigate resting ANS activity, and reactivity scores will be calculated by subtracting the mean level of activity during a resting baseline period from the mean level during a trial.

**Facial Expression.** Participants will be videotaped using a remote-controlled, high-resolution video camera in the experiment room. Trained coders will use a modified version of the Emotional Expressive Behavior coding system. Coders, who will be unaware of the nature of the trial, will code each second for ten emotional behaviors (anger, disgust, happiness/amusement, contempt, sadness, embarrassment, fear, surprise, sleepiness, confusion, and interest) on an intensity scale ranging from 0 (not present) to 3 (maximum intensity). We will sum the intensity scores for each emotional code during the most intense 30 seconds of each film.

**Subjective Experience.** Participants will be asked to report on their subjective experience before the testing session begins and after each trial. They will be asked, "Did you feel \_\_\_ while watching the movie?" and will be given the following response choices: 0= no, 1= a little, 2= moderately, 3= quite a bit, or 4= extremely.

#### Baseline questions

##### **Physical Health**

**Physical Symptoms.** Participants will indicate whether they have experienced any of the following sensations: headaches, faintness/dizziness, stomachache/pain, shortness of breath, chest pain, acne/skin irritation, runny/congested nose, stiff or sore muscles, stomach upset/nausea, irritable bowels, hot or cold spells, poor appetite, coughing/sore throat, or other in the past month. Previous studies have found this approach is a reliable and valid index of self-perceived health status. We will sum the 13 items within the report to create a total physical symptom score.

**Physical Exercise.** The Godin Leisure-Time Exercise Questionnaire will be used to measure the frequency of strenuous, moderate, and mild exercise that participants have engaged in over the past week. Body Mass Index will be calculated from height and weight measurements obtained during the laboratory visit.

**Sleep.** Selected questions from the Pittsburgh Sleep Quality Index will be used to assess subjective sleep latency, duration, calculated sleep efficiency, and overall sleep quality.

##### **Mental Health**

**Emotional Symptoms.** Participants will complete questionnaires to assess the following domains: anxiety (i.e., Generalized Anxiety Disorder- 7 Item Scale and State-Trait Anxiety State subscale), depression (i.e., Center for Epidemiologic Studies Depression Scale), obsessions and compulsions (i.e., Yale-Brown Obsessive Compulsive Scale), mania (i.e., Altman Self-Rating Mania Scale), emotion dysregulation (i.e., Difficulty in Emotion Regulation Scale), irritability (i.e., Irritability Subscale of the Buss Durkee Hostility Inventory), lability (i.e., Center for Neurological Study Lability Scale), rumination (i.e., Rumination-Reflection Questionnaire), subjective emotional experience (i.e., Positive and Negative Affect Schedule), and intensity of emotional experience (i.e., Affect Intensity Measure Simplified).

**Well-Being.** Participants will complete measures that assess their social network size and complexity (i.e., Social Network Index), loneliness (i.e., The Revised UCLA Loneliness Scale), subjective happiness (i.e., Subjective Happiness Scale), and life satisfaction (i.e., The Satisfaction With Life Scale).

**Prosociality.** We will measure trait levels of positive emotional experience (i.e., Dispositional Positive Emotions Scale), compassion (i.e., compassion subscale of the Big Five Inventory-2), and empathy (i.e., Empathic Concern subscale from the Interpersonal Reactivity Index).

#### **Aim 2. To determine whether a novel awe intervention improves subjective experience and reduces symptoms in older adults**

#### **Methods**

### ***Awe Walk Intervention***

After the laboratory assessment, participants will be randomized into one of two 8-week conditions: (1) awe condition or (2) control condition. All participants will be instructed to take a weekly 15-minute walk. In the awe condition, participants will be instructed to pay attention to the vastness and novelty of the environment around them. In the control condition, participants will receive no additional instructions.

### ***Daily questions***

#### ***Daily Emotional Experience, Life Satisfaction, Prosociality***

*Emotional Experience.* On each day of the 8-week intervention, participants will report how much they experienced awe, wonder, and amazement in addition to admiration, amusement, anger, annoyance, appreciation, anxiety, compassion, fear, happiness, pride, sadness, relaxed, and warmth. Items will be measured on 10-point Likert scales (1= not at all, 10= as much as I've ever felt).

*Life Satisfaction and Prosociality.* Participants will also respond on a daily basis to statements assessing their life satisfaction ("Today I felt that my life was... terrible to terrific") and prosociality ("How much did you engage in acts today that involved helping someone else or doing something for a good cause?"). Both items will be measured on 10-point Likert scales (1= not at all, 10= as much as I've ever felt/done). At the beginning of the study, participants will receive an email from study staff to an address the participants designate as an email in which they would like to maintain study correspondence. In this first email, there will be a personalized link in which they will open and it will direct them to the secure UCSF-supported Qualtrics platform where they can access all study questionnaires. All answers will be securely stored on the private, secure Qualtrics account managed by study staff.

### ***Post-Intervention Follow-Up Assessment***

At the conclusion of the 8-week intervention and at 3- and 6-months post-intervention, participants will again complete the physical and mental health questionnaires that they completed during their baseline visit.

Effects of Awe on Health

11/22/2016

IRB approval date: 11/22/2016

8.25 STATISTICAL METHODS: Briefly summarize the methods and types of analyses that will be performed:

We will conduct multiple regression analyses to determine whether the laboratory measures of emotional reactivity (i.e., ANS reactivity, facial expression, and self-reported experience) are associated with mental health symptoms such as anxiety and depression. We expect that greater negative emotional reactivity as

measured in the laboratory will be associated with worse mood and higher anxiety.

We will use mixed effects models to test whether the awe walk condition had beneficial effects on daily self-reported experience, life satisfaction, and prosociality. We will use analyses of covariance (controlling for age, sex, and education) to examine whether the awe walk condition resulted in decreases in anxiety and depression at the termination of the 8-week intervention and at 3- and 6-months post-intervention.

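### Must the Aim 1 regressions name covariates, a negative-reactivity score and a symptom scale before the plan can stand?

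*SAP*

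**What the plan says.** The whole analysis plan is the short text in SAP 8.25. For Aim 1 it says "We will conduct multiple regression analyses to determine whether the laboratory measures of emotional reactivity" are associated with symptoms, giving anxiety and depression as instances. It then adds a directional expectation: "We expect that greater negative emotional reactivity as" measured in the laboratory "will be associated with worse mood and higher anxiety". For Aim 2 it says "We will use analyses of covariance (controlling for age, sex, and education"), and these are the only covariates in either document.

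The Protocol, under Laboratory Assessment of Emotion, explains how scores are formed:

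- **Physiology:** nine autonomic measures, for which "reactivity scores will be calculated by subtracting the mean level of activity during a resting baseline period from the mean level during a trial".
- **Face:** "We will sum the intensity scores for each emotional code during the most intense 30 seconds of each film".
- **Self-report:** "Participants will be asked to report on their subjective experience before the testing session begins and after each trial", with post-film ratings from 0 to 4.
- **Films:** given as examples only. Two are negative (disgust and sadness) and two positive.

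Under Mental Health, the Protocol lists two anxiety scales (the GAD-7 and the state subscale of the State-Trait inventory) and one depression scale (the CES-D). Neither document defines a composite negative-reactivity score, a primary scale or a multiplicity rule for Aim 1.

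**The concern.** Two features look the wrong way round or incomplete.

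First, adjustment is spelled out for the randomised comparison, where allocation balances age, sex and education in expectation. Nothing is said for the observational regressions, where no design feature does so. If age drives both reactivity and symptoms, an unadjusted association could reflect age alone.

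Second, a directional expectation is stated, but many scores and three scales could serve as its test. If the analysts tried them all and reported whichever agreed, a reader could not tell support for the expectation from selection.

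**Working it through.** The documents state no sample size, alpha, power or effect size for Aim 1, so there is no figure to reproduce. Every n and correlation below is an assumption, used only to gauge size.

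**1. Number of candidate tests.** Scores per negative film = 9 autonomic + k facial codes + 1 self-rating. Two negative films are assumed, as in the Protocol's examples.

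- One matching facial code (k = 1): 2 × 11 = 22 scores; × 3 scales = 66 tests.
- Six negative codes (anger, disgust, contempt, sadness, embarrassment, fear; k = 6): 2 × 16 = 32 scores; × 3 = 96 tests.
- All eleven listed codes (k = 11): 2 × 21 = 42 scores; × 3 = 126 tests. This counts happiness, interest, sleepiness and similar codes as negative reactivity, so it is not a fair ceiling.

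**2. False positives that would support the expectation.** Assume two-sided 5% tests with all nulls true. Expected rejections are 66 × 0.05 = 3.3 and 96 × 0.05 = 4.8. The expectation has a direction, so once each score is signed only half of these agree with it: 66 × 0.025 = 1.65 and 96 × 0.025 = 2.4.

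For the chance of at least one supportive rejection, take equicorrelated normal statistics with correlation ρ. Given the common factor u, each test rejects in the predicted direction with probability q(u) = 1 − Φ[(1.96 − √ρ·u)/√(1 − ρ)]. The chance is 1 − E[(1 − q(u))^m].

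| Tests m | ρ = 0.5, either direction | ρ = 0.5, predicted direction | ρ = 0.8, either direction | ρ = 0.8, predicted direction |
|---|---|---|---|---|
| 66 | 0.69 | 0.35 | 0.32 | 0.16 |
| 96 | 0.77 | 0.40 | 0.36 | 0.18 |

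A sparing reading of the plan, with one score per channel, one film and two outcomes, gives 3 × 2 = 6 tests. If independent, the chance is 1 − 0.95^6 = 0.26 in either direction and 1 − 0.975^6 = 0.14 in the predicted one. With all scores in one model per scale there would be three overall tests and 3 × 0.05 = 0.15 expected false positives, though an overall test has no direction.

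**3. Confounding.** Let one covariate correlate a with both reactivity and symptoms, with no association left after adjustment. The marginal correlation is then a²: 0.04, 0.09 and 0.16 for a = 0.2, 0.3 and 0.4. By Fisher's z, an unadjusted 5% test rejects in 6%, 11% and 23% of studies at n = 60, and in 9%, 25% and 62% at n = 200. In each case the marginal correlation is not zero. The SAP predicts only that the variables are associated, so these rejections are correct for that statement. They would mislead only if read as an effect independent of the covariate, which the SAP does not claim.

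**4. What tighter specification would cost.** Power for a partial correlation of 0.3 by Fisher's z, with standard error 1/√(n − k − 3), where k is now the number of covariates:

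| n | No covariates, α = 0.05 | 3 covariates, α = 0.05 | 3 covariates, 2 tests (α = 0.025) | 3 covariates, 6 tests (α = 0.05/6) |
|---|---|---|---|---|
| 60 | 0.65 | 0.62 | 0.51 | 0.36 |
| 100 | 0.86 | 0.85 | 0.78 | 0.64 |
| 200 | 0.99 | 0.99 | 0.98 | 0.95 |

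Adjustment is almost free. A multiplicity correction is not: one score per channel on two scales (six tests) takes power at n = 60 from 0.62 to 0.36.

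**The case for a change.** The strongest case for a change is that the gap is real and cheap to close. The same SAP text found room for the ANCOVA covariates. No fuller plan is in the documents. The autonomic scores are signed differences, and nothing says which sign means greater reactivity, so the halving in step 2 is secure only for facial and self-report scores. Even the six-test reading gives a 26% chance of some false positive if the tests are independent. If Aim 1 is exploratory, one word would say so.

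Most of this stands as description. It shows that the text is silent; it does not show that a stated rule or number is wrong. Three points weaken the step to a required change:

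- Multiple regression takes several predictors as a matter of course, so adjusting for covariates lies within the plan as written.
- Age, sex and education come from a randomised ANCOVA. Nothing in the documents shows that they are the confounders that matter for Aim 1, and the Protocol also collects exercise, body mass index and sleep. Fixing those three would be a preference.
- Choosing between a corrected confirmatory test and a broad exploratory look is a trade-off against power, and either choice is defensible.

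**Conclusion.** No change follows. The SAP leaves the Aim 1 covariates, scores and scales unstated. Analysts can sensibly fill that gap when fitting the models, and the Protocol already defines how the component scores are formed and which instruments measure anxiety and depression. The aim is worded as examining a relationship, the expectation is one of association, and no confirmatory claim is attached.

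The consequence is a limit on interpretation. An isolated significant Aim 1 result in the predicted direction is weak evidence: the chance of at least one under the null is about 16% to 40% for 66 to 96 signed tests correlated at 0.5 to 0.8. That range assumes two negative films, three scales, 5% two-sided tests and a fixed sign for each score. With independent tests, or with no sign rule for the autonomic measures, it would be higher; with fewer tests it would be lower. The randomised comparisons of Aim 2 do not depend on any of this.

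### The daily-diary mixed models name no baseline covariate; if the tested effect is average diary level, one matched baseline scale per outcome would gain precision from data already collected

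*SAP*

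**What the plan says.** SAP 8.25 gives the diary outcomes one sentence: "mixed effects models to test whether the awe walk condition had beneficial effects on daily self-reported experience", together with life satisfaction and prosociality. It names no covariate, no random-effect structure, and no effect term (average level or condition-by-time). The next sentence does name covariates, "analyses of covariance (controlling for age, sex, and education", but attaches them only to anxiety and depression.

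The protocol (Daily questions) places the diary ratings "On each day of the 8-week intervention". The emotion items are "awe, wonder, and amazement in addition to admiration, amusement, anger, annoyance, appreciation, anxiety, compassion, fear, happiness, pride, sadness, relaxed, and warmth". The prosociality item asks "How much did you engage in acts today that involved helping someone else or doing something for a good cause".

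Among the baseline questions (Mental Health), the protocol lists "subjective emotional experience (i.e., Positive and Negative Affect Schedule", the Satisfaction With Life Scale, and, under Prosociality, "We will measure trait levels of positive emotional experience (i.e., Dispositional Positive Emotions Scale" and "compassion (i.e., compassion subscale of the Big Five Inventory-2), and empathy (i.e., Empathic Concern subscale from the Interpersonal Reactivity Index". The section on post-intervention follow-up says the health questionnaires were first completed at the baseline visit. The section on the awe walk intervention places randomisation after the laboratory assessment.

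**The concern.** People differ persistently in how much awe, happiness or satisfaction they report. With up to 8 × 7 = 56 diary reports each, day-to-day noise largely averages out, and most of the variance of a person's mean is this stable between-person difference. A random intercept for person counts that variance in the standard error but does not remove it. A baseline covariate related to the person's usual level removes part of it.

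An outcome analysed over time is often adjusted for its own baseline value. That is not possible here, because no diary rating before the intervention is described. The baseline questionnaires are the natural substitute, and the SAP does not name them for these models. At stake is the precision of the Aim 2 diary comparisons. Naming the scale in advance would also prevent a choice among several candidate scales after results are seen.

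**Working it through.** The documents supplied give no figure to reproduce on this point, so the gain is worked out under stated assumptions.

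**Inputs from the documents.** Two arms; daily reports over 8 weeks, at most 56 per person; no covariate in the diary models; baseline scales as listed above.

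**Assumed inputs.** Total N of 30, 50 or 100, in equal arms. ICC of the diary item 0.5 (range 0.3 to 0.7). Completed days D = 56 (range 14 to 56). Daily errors independent (range: first-order autocorrelation 0 to 0.5). r is the within-arm correlation of the baseline scale with the person's stable diary level.

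**Formula for the average-level contrast.** With total diary variance set to 1, the variance of a person's mean is ICC + E, where E = (1 − ICC)/D for independent errors. One covariate removes ICC × r². Estimating its slope costs an expected factor (N − 3)/(N − 4) = 1 + 1/(N − 4). So

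adjusted/unadjusted variance = [ICC(1 − r²) + E] / [ICC + E] × [1 + 1/(N − 4)].

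**Base case.** E = 0.5/56 = 0.0089. The stable share of the variance is 0.5/0.5089 = 0.982. The first factor is 1 − 0.982r²: 0.912 at r = 0.3 and 0.754 at r = 0.5. The cost factors are 1 + 1/26 = 1.038, 1 + 1/46 = 1.022 and 1 + 1/96 = 1.010.

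| Assumed N | r = 0 | r = 0.3 | r = 0.5 | break-even r |
|---|---|---|---|---|
| 30 | 1.038 | 0.947 | 0.783 | 0.19 |
| 50 | 1.022 | 0.931 | 0.771 | 0.15 |
| 100 | 1.010 | 0.921 | 0.762 | 0.10 |

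Break-even follows from setting the ratio to 1: r² = 1/[(N − 3) × 0.982]. At N = 50 this is 1/(47 × 0.982) = 0.0217, so r = 0.147.

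**In other units.** At N = 50, r = 0.3 is equivalent to 50/0.931 = 53.7 participants (about 4 more; standard error √0.931 = 0.965, or 3.5% smaller). r = 0.5 is equivalent to 50/0.771 = 64.9 (about 15 more; standard error about 12% smaller). At r = 0.2 the ratio is 0.982, worth about one participant.

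**Sensitivity.** Over the full range of ICC, days and autocorrelation, the stable share runs from 69% to 99%. At N = 50 the ratio is 0.930 to 0.958 for r = 0.3 and 0.768 to 0.846 for r = 0.5. At N = 100 it is 0.920 to 0.948 and 0.760 to 0.836. The worst-case break-even r is 0.23, 0.18 and 0.12 for N = 30, 50 and 100.

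**Check by simulation** (8,000 runs). The level ratio was 0.931 (r = 0.3) and 0.776 (r = 0.5) at N = 50, and 0.925 and 0.770 at N = 100. The mean adjusted effect was within 0.006 of the true zero.

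**Condition-by-time contrast.** With individual slopes simulated independently of baseline, the variance ratio for the slope difference was 1.018 to 1.024 at N = 50 and 1.009 to 1.012 at N = 100. That is no gain, only the cost of the extra term. The same cost factor gives about 4% at N = 30.

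**The case against.** The strongest reply is that this is an optional efficiency choice. SAP 8.25 answers a form field that asks for a brief summary, so silence does not show that covariates will be left out. That is fair as to intent. Even so, the same paragraph names covariates for one Aim 2 analysis and none for the other, so naming them here is within its own level of detail.

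Second, the size of the gain rests wholly on assumed values. This stands. Gains near break-even are trivial, and nothing in the documents shows that r reaches 0.3. A broad trait scale may also track a single item such as fear or pride less well than a composite.

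Third, the covariate is secondary to a question that the SAP leaves open: whether benefit means a higher average level or a different course over time. This also stands.

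Fourth, completion of the scales before allocation is likely but not explicit. The protocol also describes a personal link, emailed when the study starts, that gives access to all of the questionnaires. The timing therefore has to be confirmed.

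Fifth, standard software drops anyone with a missing covariate. Losing one participant of 50 costs 50/49 − 1 = 2%, enough to cancel the gain at r = 0.2 (0.982 × 1.020 = 1.002). A rule for missing scores is needed.

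A reader might infer that the planned comparison is biased or invalid without the covariate. It is not: randomisation protects the unadjusted contrast. Nor should a reader infer that the trial has no sample size, since a passage was removed before review.

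**Conclusion.** The point holds as a precision improvement, conditional on the arm difference in average diary level being the tested effect. Under ICC 0.5 and 56 completed days, one matched scale cuts the variance by about 5% to 8% at r = 0.3 and 22% to 24% at r = 0.5, over N from 30 to 100. If the scale proves unrelated, or the test is condition-by-time with slopes unrelated to baseline, it costs about 4%, 2% or 1% at N = 30, 50 or 100.

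The match is closest for life satisfaction, reasonable for emotion, and loose for prosociality, where trait scales would be paired with acts done that day. It would be tempting to report a definite loss of power or a threshold for this trial. The documents support neither, because N, ICC and r are all assumed.

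**What to change.** Add to SAP 8.25 that each diary model includes one pre-specified fixed baseline covariate:

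- Satisfaction With Life Scale for daily life satisfaction;
- Dispositional Positive Emotions Scale for the positive emotion items or their composite;
- PANAS negative affect for the negative items (anger, annoyance, anxiety, fear and sadness) or their composite.

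For prosociality a covariate is optional. If one is used, name a single trait scale in advance.

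Confirm that the scales are completed before allocation, and use only scores that were. Keep participants with a missing score in the model by a simple rule, such as imputing the overall mean of the covariate, so that no one is dropped. Do not use early diary days as a baseline, because they follow randomisation. State in advance whether average level or condition-by-time is the test of benefit; this change does not settle that choice.

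The cost is SAP wording, a check of questionnaire timing, and one extra model term per outcome. No new data are needed.

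### The Aim 2 ANCOVAs leave the outcome (follow-up score or change) undefined and omit the baseline score already collected on the same scale; adding it sharpens the comparison and settles which analysis is meant

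*SAP*

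**What the plan says.** SAP section 8.25 covers the anxiety and depression comparison in one sentence: "analyses of covariance (controlling for age, sex, and education) to examine whether the awe walk condition resulted in decreases in anxiety and depression". The comparison is made three times, once when the intervention finishes and again 3 and 6 months later. The covariates are named, and baseline severity is not one of them. The only hint about the form of the outcome is that the condition is to have "resulted in decreases in anxiety and depression at the termination of the 8-week intervention".

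The protocol shows that baseline scores will exist. Under Mental Health, within the baseline questions, anxiety is measured by the "Generalized Anxiety Disorder- 7 Item Scale and State-Trait Anxiety State subscale" and the depression instrument is given as "depression (i.e., Center for Epidemiologic Studies Depression Scale". The Post-Intervention Follow-Up Assessment section says that, at all three follow-ups, "participants will again complete the physical and mental health questionnaires that they completed during their baseline visit". On timing, the Awe Walk Intervention section says: "After the laboratory assessment, participants will be randomized into one of two 8-week conditions".

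Neither document defines the dependent variable or adds a covariate anywhere else.

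**The concern.** Two analyses fit the SAP sentence: the follow-up score adjusted for age, sex and education, or the change from baseline adjusted for the same three. They are different estimators. With identical regressors, the change-score estimate equals the follow-up-score estimate minus the covariate-adjusted difference between the arms at baseline. Any chance imbalance at baseline therefore pulls the two results apart, and the plan does not say which will be reported.

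Both also discard information. The earlier score on a scale usually predicts the later one, and it does so in a model where age, sex and education may explain little. Leaving it out widens the confidence interval for the awe effect on each of three scales at each of three visits (3 × 3 = 9 comparisons) and leaves chance baseline differences in severity without proper adjustment.

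**Working it through.** **Inputs.** From the documents: ANCOVA with three covariates, two randomised arms, and the same scales at baseline and at three follow-ups. The documents state no sample size, effect size, standard deviation, correlation or allocation ratio, so there is no figure of the plan's own to reproduce. Assumed here: equal SD at baseline and follow-up, 1:1 allocation, and a baseline-to-follow-up correlation r from 0.3 to 0.8. Except in step 2, r is the correlation given age, sex and education.

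**Step 1: residual variance in SD² units.** Follow-up score: 1. Change score: 2(1 − r). Either outcome with baseline as covariate: 1 − r². Hence adjusted/follow-up = 1 − r² and change/adjusted = 2(1 − r)/(1 − r²) = 2/(1 + r).

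| r | Adjusted / follow-up variance | SE reduction, 1 − √(1 − r²) | Change / adjusted variance | SE reduction, 1 − √((1 + r)/2) |
|---|---|---|---|---|
| 0.3 | 0.91 | 5% | 1.54 | 19% |
| 0.5 | 0.75 | 13% | 1.33 | 13% |
| 0.7 | 0.51 | 29% | 1.18 | 8% |
| 0.8 | 0.36 | 40% | 1.11 | 5% |

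The two readings also differ from each other: the change score has 1.40, 1.00 and 0.60 times the variance of the follow-up score at r = 0.3, 0.5 and 0.7.

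**Step 2: allowing for the planned covariates.** Now let r be the raw correlation, and suppose age, sex and education explain a share c = 0.10 of both scores through the same composite. The partial correlation is (r − c)/(1 − c) = 0.222, 0.444, 0.667, 0.778. The follow-up-score factor, 1 minus its square, becomes 0.95, 0.80, 0.56, 0.40. The gain shrinks slightly and remains.

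**Step 3: power, for illustration only.** Assume 50 per arm, a true effect of 0.4 SD and a two-sided 5% test. The noncentrality is 0.4/√(2/50) = 2.0 for the follow-up score, divided by the square root of the relative variance for the other two. Degrees of freedom are 95 without baseline and 94 with it.

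| r | Follow-up score | Change score | Baseline-adjusted |
|---|---|---|---|
| 0.3 | 51% | 39% | 55% |
| 0.5 | 51% | 51% | 63% |
| 0.7 | 51% | 72% | 79% |

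**Step 4: cost of the extra covariate.** With three covariates already in the model and total sample N, one more inflates variance by (N − 6)/(N − 7): 34/33, or 3.0%, at N = 40; 54/53, or 1.9%, at N = 60; 94/93, or 1.1%, at N = 100. Against the follow-up score this is repaid once r² exceeds 1 − (N − 7)/(N − 6), that is, |r| above about 0.17, 0.14 and 0.10.

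**Step 5: does adding baseline remove the ambiguity?** Write B for baseline, Y for follow-up and T for arm. Modelling Y − B on T, B and the demographics with coefficient b on B is the same as modelling Y with coefficient b + 1. The coefficient on T is unchanged. Without B, the two estimates differ by the adjusted baseline difference, whose standard deviation at 50 per arm is about √(2/50) = 0.2 SD, half the effect assumed in step 3.

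**Step 6: simulation.** With 50 per arm, r = 0.3, 0.5 or 0.7, c = 0 or 0.10 and 6000 replicates per setting, a true effect of −0.40 gave mean estimates between −0.397 and −0.404 for every analysis. Type I error was 0.044 to 0.054. Neither reading is biased. With baseline included, the follow-up and change estimates agreed to within 2 × 10⁻¹⁵ in every replicate. A separate run of 4000 replicates at N = 60 and r = 0.5 gave adjusted variance 0.78 times that of the follow-up score and 0.76 times that of the change score. At r = 0 the ratio to the follow-up score was 1.02, in line with step 4.

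**The case against.** The form behind section 8.25 asks only for a brief summary, so baseline adjustment may have been intended and simply left out. The reference to decreases also suggests a change score. On that reading baseline already enters the analysis, and where r is high there is little left to gain: 8% off the standard error at r = 0.7 and 5% at 0.8. Correlations could also be lower than assumed. One anxiety measure is a state scale, the last follow-up comes about eight months after baseline, and the baseline visit includes emotion-eliciting films. At r = 0.1 the follow-up-score gain is only 0.5% of the standard error, roughly cancelled by the lost degree of freedom in a small trial. Finally, the planned comparison is valid as it stands.

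Much of this is fair, and it limits the size of the point. It does not fill the gap. The summary does list covariates by name, and a reader would take the list as complete. The change score is never stated, and without baseline as a covariate it is still less precise than the adjusted analysis at every r in the range; below r = 0.5 it is worse than the plain follow-up score.

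Two further remarks stand. The protocol implies, but does not state outright, that the baseline questionnaires are completed before allocation; the Daily questions section describes an emailed link to the study questionnaires at the start of the study. And baseline adjustment does not decide which anxiety scale or visit carries the claim, nor how a missing baseline score is handled.

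**Conclusion.** The concern holds. The outcome is undefined and the same-scale baseline score is not among the listed covariates, although it is collected. No bias follows: the loss is precision, together with an open choice between two analyses that can give different answers from the same data. Over assumed correlations of 0.3 to 0.8, adding baseline cuts variance by 9% to 64% relative to the follow-up score and by 35% to 10% relative to the change score. The gain is small at the low end for the first reading and at the high end for the second. These figures rest on equal SDs at the two times, a single correlation applied to all follow-ups, and a baseline measured before randomisation. The power figures also depend on the illustrative 50 per arm and 0.4 SD. The point is worth fixing because adjustment improves on both readings across this range at almost no cost.

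**What to change.** Replace the covariate statement in SAP section 8.25 with wording such as:

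> The outcome is the follow-up score. Each analysis of covariance adjusts for the pre-randomisation baseline score on the same scale and for age, sex and education.

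Confirm in the protocol that the baseline questionnaires are completed before allocation, and add a line on how a missing baseline score will be handled. Modelling the three follow-up visits jointly is optional.

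The cost is a change of wording and one degree of freedom per model. No new data are needed, since the baseline questionnaires are already part of the study.
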